### **5.5.1 Reasons for Withdrawal**

In addition to discontinuation from therapy related to toxicities as outlined in the Halting Rules of Section 9.5, a subject will also be discontinued from protocol therapy and followed up per protocol under the following circumstances:

- Documented disease progression
- The treating physician thinks a change of therapy would be in the best interest of the subject.
- The subject requests to discontinue protocol therapy, whether due to unacceptable toxicity or for other reasons.
  - If a subject decides to prematurely discontinue protocol therapy (“refuses treatment”), the subject should be asked if he or she may still be contacted for further scheduled study assessments. The outcome of that discussion should be documented in both the medical records and in the electronic case report form (eCRF).
- A female subject becomes pregnant.
- The subject meets an exclusion criterion (either newly developed or not previously recognized) that precludes further study participation.

Subjects will be removed from protocol therapy and the site investigator notified when any of the criteria listed above apply. The reason for discontinuation of protocol therapy will be documented on the eCRF.

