### **5.5.2 Handling of Subject Withdrawals or Subject Discontinuation of Study Intervention**

If a subject decides to withdraw from the study (and not just from protocol therapy) all efforts should be made to complete and report study assessments as thoroughly as possible. The study team should contact the subject or a responsible relative by telephone to establish as completely as possible the reason for the study withdrawal. A complete final evaluation at the time of the subject's study withdrawal should be made with an explanation of why the

subject is withdrawing from the study. If the reason for removal of a subject from the study is an adverse event, it will be recorded on the eCRF.

If a subject is unevaluable for safety and efficacy endpoints (i.e., lacks molecular/correlative studies, and creation of PDXs, subject has not received both cetuximab doses in their entirety and/or has not had surgical resection of the tumor), then the subject will be replaced at the discretion of the principal investigator.

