### **6.2.1 Potential adverse events and precautions**

#### *Infusion Reactions*

Serious infusion reactions can occur during cetuximab administration. Serious infusion reactions include rapid onset of airway obstruction (bronchospasm, stridor, hoarseness), hypotension, shock, loss of consciousness, myocardial infarction, and/or cardiac arrest. Severe (NCI CTC Grades 3 and 4) infusion reactions occurred in 2–5% of patients in prior clinical studies with a fatal outcome in 1 patient [Cetuximab FDA prescribing information].

Approximately 90% of severe infusion reactions occurred with the first infusion despite premedication with antihistamines. Thus, patients must be monitored for at least 1 hour following cetuximab infusions in a setting with resuscitation equipment and other agents necessary to treat anaphylaxis (e.g., epinephrine, corticosteroids, intravenous antihistamines, bronchodilators, and oxygen). For any subjects who experience an infusion reaction, longer monitoring may be necessary and is appropriate to confirm resolution of the event.

In the event of an infusion reaction,

- For NCI CTC grade 1, grade 2, and non-serious grade 3 infusion reaction, cetuximab will be temporarily held with administration of emergency medications as appropriate by the treating physician. Upon resolution of the infusion reaction, subjects may be rechallenged with cetuximab at a reduced infusion rate.
- For serious grade 3 and all grade 4 infusion reactions, cetuximab will be permanently discontinued.
- All subjects should receive appropriate medical intervention as appropriate by the treating physician
- Emergency medications to be available in the event of an infusion reaction include:
  - Diphenhydramine 25-50 mg IV
  - Dexamethasone 4-10 mg IV
  - Albuterol nebulization solution 2.5 mg/3ml

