#### *Dermatologic Toxicity*

Dermatologic toxicities, including acneiform rash, skin drying and fissuring, paronychial inflammation, infectious sequelae (for example, *S. aureus* sepsis, abscess formation, cellulitis, blepharitis, conjunctivitis, keratitis/ulcerative keratitis with decreased visual acuity, cheilitis), and hypertrichosis occurred in patients receiving cetuximab therapy. Acneiform rash occurred in 76–88% of 1373 patients receiving cetuximab. Severe acneiform rash occurred in 1–17% of patients. Acneiform rash usually developed within the first two weeks of therapy and resolved in a majority of the patients after cessation of treatment, although in nearly half, the event continued beyond 28 days.

- Study subjects will be monitored for dermatologic toxicities and infectious sequelae.
- Subjects will be instructed to limit sun exposure during cetuximab treatment
- Severe (NCI CTC Grade 3 or 4) acneiform rash will result in discontinuation of cetuximab therapy.

- Intolerable grade 2 rash, despite maximum supportive care, will result in discontinuation.
- NCI CTC Grade 1 or 2 rash is to be treated with one or more of the following medications at the treating physician's discretion, based upon supportive care evidence. Potential medications that can be used for the treatment of cetuximab-related rash may include, but are not limited to, the following:
  - Hydrocortisone 1 to 2.5% lotion
  - Doxycycline 100 mg bid
  - Clindamycin 1% lotion

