### **6.3 Modification of Study Product Administration for a Subject**

#### **Dose Delays/Dose Modifications**

- No dose modifications will be planned. Please refer to section 6.2.1 (subsection, Infusion Reactions) for more information regarding infusion rate decreases in the setting of infusion reaction.
- Dose delays secondary to intolerance (such as infusion reactions) are permitted. Subjects can be rechallenged with cetuximab within 3 days but will otherwise be discontinued from the study.
- Expected adverse events that would delay cetuximab infusion:
  - Grade 3 or higher nausea, vomiting, diarrhea, stomatitis, or rash uncontrolled despite maximal medical management due to a toxicity that is considered at least PROBABLY related to study treatment
  - Any other Grade 3 or higher non-hematologic toxicity, except grade 3 fatigue lasting >7 days, due to a toxicity that is considered at least PROBABLY related to study treatment
  - Grade 3 or 4 electrolyte abnormalities that are corrected within 48 hours will not be considered a serious adverse event.

---

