### 7.4 Withdrawal Visit

If a subject decides to withdraw from the study (and not just from protocol therapy) all efforts should be made to complete and report study assessments as thoroughly as possible. The treating investigator should contact the subject or a responsible relative by telephone to establish as completely as possible the reason for the study withdrawal. A complete final evaluation at the time of the subject's study withdrawal should be made with an explanation of why the subject is withdrawing from the study. If the reason for removal of a subject from the study is an adverse event, it will be recorded on the eCRF.

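### Sections 6.3 and 5.5.2, read literally, could remove cetuximab-intolerant subjects from the safety evaluation that 5.5.1 and 12.2 keep them in (minor)

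*Combined protocol and SAP*

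**What the plan says.** **Follow-up after a toxicity stop.** Section 6.3 allows dose delays for intolerance such as infusion reactions, then adds: "Subjects can be rechallenged with cetuximab within 3 days but will otherwise be discontinued from the study". Section 5.5.1 takes a different line for subjects who stop treatment: "a subject will also be discontinued from protocol therapy and followed up per protocol under the following circumstances". Its list includes a physician's decision to change therapy and a subject's request to stop because of toxicity. The protocol separates leaving the study from leaving treatment; section 7.4 (and 5.5.2 in the same terms) begins "If a subject decides to withdraw from the study (and not just from protocol therapy". For the more severe toxicities, section 6.2.1 speaks only of the drug: "For serious grade 3 and all grade 4 infusion reactions, cetuximab will be permanently discontinued", and grade 3 or 4 "acneiform rash will result in discontinuation of cetuximab therapy". It says nothing about study status.

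**Who counts for safety.** Section 5.5.2 begins a replacement rule with "If a subject is unevaluable for safety and efficacy endpoints" and lists among the grounds "subject has not received both cetuximab doses in their entirety". Section 12.2 includes in the safety evaluation everyone who has a research biopsy. It asks for both full doses and resection only for efficacy, molecular and correlative work, and xenografts.

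**The endpoint concerned.** The only secondary endpoint (3.2.2) is hospital readmission for wound care or surgical complications attributed to cetuximab within 28 days after surgery. Section 12.4 reports it as a proportion with an exact 95% confidence interval and names no denominator.

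**The concern.** Safety of pre-operative cetuximab is the sole secondary objective, and the subjects touched by these two rules are those who tolerated the drug poorly. If 6.3 is applied as written, such a subject could leave before the 28 days after surgery have run. The outcome is then missing or, if nobody looks for it, counted as no event. If 5.5.2 is applied as written, a subject with one full dose who goes on to surgery can be treated as unevaluable for safety and replaced. Under 12.2 the same subject counts. Replacement is at the principal investigator's discretion, so the choice between the two readings could be made after outcomes are known.

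**Working it through.** **1. The texts side by side, for a subject who had dose 1, was not rechallenged in time and then had surgery**

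| Question | One section | Another section |
|---|---|---|
| Still followed? | 6.3: out of the study | 5.5.1: off therapy, followed per protocol (through its toxicity and physician-decision items) |
| Evaluable for safety? | 5.5.2: no, both full doses are needed | 12.2: yes, a research biopsy is enough |
| SAEs recorded to 28 days after surgery? | 9.2 and 9.4: yes, no exemption stated | 6.3: does not say how this continues for someone out of the study |

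The second row is a conflict on the face of the text. The first needs a step of inference, because the list in 5.5.1 does not mention a missed rechallenge.

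**2. The plan's own figure.** Section 12.2 gives 36 subjects for 20% versus 65% response, a 1:2 split of high to low AXL, 90% power and one-sided 5%. The unpooled normal approximation for the smaller group is (1.645 + 1.282)² × (0.20 × 0.80 + 0.65 × 0.35 / 2) / 0.45² = 11.6. That rounds up to 12, with 24 in the other group, total 36. This is a count of subjects for the response comparison. Neither safety rule enters it, so the sample size and power do not change.

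**3. Loss of outcome under 6.3 (illustration).** Assumptions, none given in the documents: 36 subjects treated and operated, k = 1 to 3 of them removed with outcome unknown, and no readmissions among the rest. The exact (Clopper-Pearson) limits for x events in n are the 2.5% point of Beta(x, n − x + 1) and the 97.5% point of Beta(x + 1, n − x).

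- Missing counted as no event: 0/36 = 0% (95% CI 0 to 9.7%).
- Every missing outcome in fact a qualifying readmission: 1/36 = 2.8% (0.1 to 14.5%), 2/36 = 5.6% (0.7 to 18.7%), 3/36 = 8.3% (1.8 to 22.5%).

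The largest possible understatement is k/36, or 2.8 to 8.3 percentage points. It is a ceiling, not an expectation.

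**4. Replacement under 5.5.2 (illustration).** Assumptions: 36 completers with no event, plus one under-dosed, operated and replaced subject who has the only readmission.

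- Subject counted: 1/37 = 2.7% (0.1 to 14.2%).
- Subject left out: 0/36 = 0% (0 to 9.7%).

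**5. Is the biopsied set the right denominator?** The research biopsy is a Step 1 procedure (5.1). Sections 4 and 5.2 provide for biopsied people who never reach treatment. Section 5 expects about 100 screened for 36 enrolled. At the extreme where all 100 had a biopsy (an assumption), three readmissions would be 3/100 = 3.0%, against 3/36 = 8.3% among those treated and operated. Simply applying 12.2's set to a post-surgical cetuximab endpoint could therefore dilute the rate.

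**The case against.** The strongest reply has three parts.

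*The wording is loose, not contradictory.* The 6.3 sentence is a dose-delay bullet in a section on giving the drug, so it may have meant study treatment. Section 5.5.1 does not list a missed rechallenge, and its lead-in, "In addition to discontinuation from therapy related to toxicities as outlined in the Halting Rules of Section 9.5", treats toxicity stops as stops of therapy. This is fair, and it makes the first conflict an inference. But 6.3 says study, and the protocol elsewhere distinguishes study from therapy deliberately.

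*Section 5.5.2 is a replacement rule.* It does not say that a replaced subject's safety data are discarded, and 12.2 is where the analysed set is stated. This also stands. A reader might infer that the plan excludes under-dosed subjects from the safety analysis; the documents support only that 5.5.2 labels them unevaluable for safety, in conflict with 12.2.

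*SAE recording covers the harm.* Inpatient hospitalization is an SAE (9.1.3), and SAEs are recorded to at least 28 days after surgery with no stated exemption for subjects off drug. Surgery and the one-month visit are standard of care at a single site. Most readmissions would probably be found. Recording the event still does not settle whether the subject belongs in the denominator.

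Two further inferences are not supported. One is that the readmission rate will be biased downward: intolerant subjects also received less drug, so the direction is plausible but not shown. The other is that 6.3 should state that its 3 days run from the held infusion: dose 2 already has a window of 7 days plus or minus 3, which the 3 days may simply mirror, and fixing the start could permit dosing outside that window.

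**Conclusion.** The point holds as a minor inconsistency in two stated rules. The 5.5.2 against 12.2 conflict on safety evaluability is direct; the 6.3 against 5.5.1 conflict on follow-up is a fair reading that relies on 5.5.1's toxicity and physician-decision items. The step 3 ceiling rests on assumed values for the number lost and the number operated, and it falls to zero if SAE recording captures the events. The step 4 difference of 2.7 points rests on a single hypothetical subject. What remains in all cases is that the readmission proportion has no settled denominator for under-dosed subjects. The primary endpoint is untouched.

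**What to change.** 1. In 6.3, replace the closing consequence with: *discontinued from cetuximab and followed per 5.5.1, including readmissions and SAEs through 28 days after surgery*.
2. In 5.5.2, delete the words *safety and*, so that under-dosed subjects stay in the safety evaluation even when they are replaced for efficacy.
3. In 12.4, state the denominator of the readmission proportion: every subject who received any cetuximab and had surgery. The biopsied set in 12.2 can remain for the general description of adverse events.

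An editorial correction can go in at the same time: 5.5.1 refers toxicity stops to 9.5, which contains only a study-level enrollment suspension rule. The subject-level rules are in 6.2.1 and 6.3.

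The cost is a few wording changes, with no extra patients, visits or dosing rules. The one-month visit has a window of plus or minus 2 weeks, so it can fall as early as Day 14 to 17 after surgery (28 to 31 days minus 14). For a subject seen before Day 28, a chart check completes the period, and SAE recording under 9.2 already runs that long.

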### **9.1.3 *Serious Adverse Events***

A serious adverse event (SAE) is one that meets one or more of the following criteria:

- Results in death
- Is life-threatening (places the subject at immediate risk of death from the event as it occurred)

- Results in inpatient hospitalization or prolongation of existing hospitalization
- Results in a persistent or significant disability or incapacity
- Results in a congenital anomaly or birth defect
- An important medical event that may not result in death, be life threatening, or require hospitalization may be considered an SAE when, based upon appropriate medical judgment, the event may jeopardize the subject and may require medical or surgical intervention to prevent one of the outcomes listed in this definition.

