### **Procedures for Recording and Reporting Serious Adverse Events**

- SAEs will be reported from time of informed consent until 28 days after discontinuation of cetuximab or definitive surgery, whichever is later.
- Any SAEs experienced after this 28-day period will only be reported if the investigator suspects a causal relationship (possibly, probably or definitely related) to the study treatment.
- SAEs will be reported on the SAE Submission Form and entered in SAE tab in OnCore within 1 business day of discovery of the event.
- SAEs include events related and unrelated to the study drug(s).
- SAEs will be recorded in the subject's medical record and on the appropriate study specific eCRF form within OnCore.
- All SAEs, regardless of relation to study drug, will be followed until resolution to ≤ Grade 1 or baseline and/or deemed clinically insignificant and/or until a new anti-cancer treatment starts, whichever occurs first.
- Recurrent episodes, complications, or progression of the initial SAE will be reported as follow-up to the original episode within 24 hours of the investigator receiving the follow-up information.

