### **Expedited Reporting of Serious Adverse Events**

Depending on the nature, severity, and attribution of the serious adverse event an SAE report will be phoned in, submitted in writing, or both according to Table 1 below. All serious adverse events must also be reported to the UWCCC Data and Safety Monitoring Committee Chair. All serious adverse events must also be reported to the UW IRB (if applicable), and any sponsor/funding agency not already included in the list.

Determine the reporting time line for the SAE in question by using the following table.

**Table 1. Expedited Reporting Requirements for Adverse Events that Occur in Non-IND/IDE Studies Within 28 Days Post Surgical Intervention**

Reporting Requirements for Serious Adverse Events
--

**NOTE:** Investigators MUST immediately report to the *UWCCC DSMC, NIDCR (via Rho) and the IRB (if applicable)* ANY Serious Adverse Events, whether or not they are considered related to the investigational agent(s)/intervention. See below.

An adverse event is considered serious if it results in ANY of the following outcomes:

- 1) Death.
- 2) A life-threatening adverse event.
- 3) An adverse event that results in inpatient hospitalization or prolongation of existing hospitalization for  $\geq 24$  hours.
- 4) A persistent or significant incapacity or substantial disruption of the ability to conduct normal life functions.
- 5) A congenital anomaly/birth defect.
- 6) Important Medical Events (IME) that may not result in death, be life threatening, or require hospitalization may be considered serious when, based upon medical judgment, they may jeopardize the patient or subject and may require medical or surgical intervention to prevent one of the outcomes listed in this definition (FDA, ICH E2A and ICH E6).

**ALL SERIOUS adverse events that meet the above criteria\* MUST be immediately reported to the UWCCC within the timeframes detailed in the table below:**

Hospitalization	Grade 1 Timeframes	Grade 2 Timeframes	Grade 3 Timeframes	Grade 4 & 5 Timeframes
Resulting in hospitalization <math>\geq 24</math> hrs		10 Calendar Days		24-Hour; 5 Calendar Days
Not resulting in Hospitalization <math>\geq 24</math> hrs	Not required		10 Calendar Days	

*\*Hospitalization for planned surgical resection does not require reporting\**

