#### **9.4.2 Serious Adverse Event Reporting to NIDCR**

Any AE meeting the specified Serious Adverse Event criteria will be submitted on an SAE form to NIDCR's centralized safety system via Rho Product Safety. This report may be sent by fax or email. Once submitted, Rho Product Safety will send a confirmation email to the investigator within 1 business day. The investigator should contact Rho Product Safety if this confirmation is not received. This process applies to both initial and follow-up SAE reports.

SAE Reporting Contact Information:

- Product Safety Fax Line (US): [name]
- Product Safety Fax Line (International): [contact]
- Product Safety Email: rho\[contact]

General questions about SAE reporting can be directed to the Rho Product Safety Help Line (available 8:00AM – 5:00PM Eastern Time):

- US: [name]
- International: [contact]

The study clinician will complete a Serious Adverse Event Form and submit via fax or email within the following timelines:

- All deaths and immediately life-threatening events, whether related or unrelated, will be recorded on the Serious Adverse Event Form and submitted to Product Safety within 24 hours of site awareness.
- Serious adverse events other than death and immediately life-threatening events, regardless of relationship, will be reported by fax within 10 calendar days of site awareness.

All SAEs will be followed until resolution or stabilization.

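### Section 6.3 denies SAE status to grade 3 or 4 electrolyte abnormalities corrected within 48 hours, which contradicts section 9 for the narrow subset that meets a seriousness criterion

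*Combined protocol and SAP*

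**What the plan says.** The statement is the last bullet of a list in section 6.3, under Dose Delays/Dose Modifications, headed "Expected adverse events that would delay cetuximab infusion". It reads: "Grade 3 or 4 electrolyte abnormalities that are corrected within 48 hours will not be considered a serious adverse event". It has no qualifier for outcome.

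Section 9.1.3 makes an event serious if it meets at least one outcome criterion. Two matter here: that the event is life-threatening, and "Results in inpatient hospitalization or prolongation of existing hospitalization". Table 1 in section 9.4 repeats the outcome list but sets the hospitalization criterion at 24 hours or more. It says that all events meeting its criteria "MUST be immediately reported to the UWCCC within the timeframes detailed in the table below". The only exemption noted beneath it is the hospital stay for the planned resection.

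Section 9.4.2 says: "Any AE meeting the specified Serious Adverse Event criteria will be submitted on an SAE form". Deaths and immediately life-threatening events are to be "submitted to Product Safety within 24 hours of site awareness". Other SAEs, "regardless of relationship, will be reported by fax within 10 calendar days of site awareness".

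Section 9.4 also requires SAEs to be "entered in SAE tab in OnCore within 1 business day of discovery of the event". Section 9.5 suspends enrollment for further analysis if more than 25% of subjects have SAEs probably related to cetuximab.

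**The concern.** Grade measures severity, while seriousness is defined by outcome. A rule that sets seriousness from grade and speed of correction can therefore disagree with the outcome definition. The event type is foreseeable: section 9.1 lists low magnesium, potassium and calcium among the common cetuximab toxicities, and section 6.2.1 requires them to be monitored.

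At stake are the classification and expedited reporting of a possibly small number of events, and the one stopping guideline in the protocol that counts SAEs. A coordinator who followed the electrolyte-specific sentence would be applying the protocol as written, and so would one who followed section 9.

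**Working it through.** The plan states no figure to reproduce. The check sets the rules side by side for each kind of grade 3 or 4 electrolyte abnormality corrected within 48 hours.

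| Event | 6.3 | 9.1.3 and 9.4.2 | Table 1 | Conflict |
|---|---|---|---|---|
| Repleted, no outcome criterion met | Not an SAE | Not an SAE | Not an SAE | None |
| Admitted for under 24 hours, no other criterion met | Not an SAE | SAE | Not an SAE | With 9.1.3 and 9.4.2 only |
| Admitted for 24 hours or more | Not an SAE | SAE | SAE | Full |
| Life-threatening, with or without admission | Not an SAE | SAE | SAE | Full |

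The third row needs nothing unusual: a stay of 24 to 48 hours for repletion satisfies both the 48-hour condition in 6.3 and the 24-hour threshold in Table 1. Section 9 does not refer to 6.3, and 6.3 does not refer to section 9.

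**What an affected event could lose if 6.3 is followed:**

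- the SAE label, and with it the OnCore SAE entry due within 1 business day (section 9.4);
- SAE reporting to the UWCCC DSMC, on either the 24-hour route with a full report within 5 calendar days or the 10-calendar-day route, and the IRB report within 10 calendar days where applicable (section 9.4);
- its place in the halting count, provided it is probably related and is that subject's only qualifying SAE (section 9.5).

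**What is kept.** Before surgery the event is still recorded as an AE (sections 9.2 and 9.4), and the principal investigators review probably attributed AEs weekly (section 9.5).

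**Halting count.** The rule needs a proportion above 25%, so the smallest suspending count among n subjects is floor(n/4) + 1.

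- n = 36: floor(36/4) + 1 = 10. 10/36 = 27.8% suspends; 9/36 = 25.0% does not.
- n = 12: floor(12/4) + 1 = 4. 4/12 = 33.3% suspends; 3/12 = 25.0% does not.

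Reclassifying one subject changes the result only when the count stands exactly at that smallest value.

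**Endpoints.** The primary endpoint is tumor response by clinical measurement. The secondary endpoint counts readmissions for wound care or surgical complications attributed to cetuximab. Neither uses the SAE label, and the sample size does not depend on it.

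**The case against.** The best defense is context. The bullet belongs to a list of reasons to delay an infusion. The bullet before it delays dosing for any other probably related non-hematologic toxicity of grade 3 or higher, so an exception for quickly corrected electrolytes would fit naturally there. Section 9.1 sends AE and SAE reporting to section 9.4, and the SAE evaluation at the 1-month visit cites section 9.1, so staff would probably use the outcome definition.

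This makes a benign intention plausible but does not resolve the text. The sentence speaks of SAE status and never mentions delay. If a dosing exception was meant, it has not been delivered, because the preceding bullet still applies to a probably related abnormality. No text settles which section governs.

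Two stronger readings are tempting and should not be adopted.

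- **That the NIDCR report is lost.** The duty in 9.4.2 attaches to any AE that meets the criteria, and immediately life-threatening events are named there. It can be read as surviving removal of the label, so the report is put in conflict, not clearly lost.
- **That events after surgery would disappear from the study data.** A reader might infer this because AE recording normally closes on the day of surgery, leaving only the SAE route. But no study infusion remains to be delayed after surgery, so applying this bullet there is speculative. Appendix A schedules no serum chemistry after Visit 5. Electrolyte abnormalities are noted in the medical record (section 6.2.1), which is a source document (section 13), and a readmission could surface at the 1-month assessment (section 4). Nor can any such loss be confined to the 28 days after surgery, because sections 9.2 and 9.4 keep related SAEs reportable beyond that.

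**Conclusion.** The statement in 6.3 is wrong as written, and the matter is minor. It contradicts 9.1.3 and 9.4.2 for rapidly corrected electrolyte abnormalities that meet an outcome criterion, and Table 1 as well, except where the only criterion met is an admission of under 24 hours. A reader might infer that every rapidly corrected grade 3 or 4 abnormality is being misclassified; that does not follow, because without a qualifying outcome the sections agree.

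The number of affected events cannot be estimated from the documents and may be zero. The reporting consequences assume that staff follow 6.3 over section 9. The halting consequence needs, in addition, a probably related event, no other qualifying SAE in that subject, and a count exactly at the threshold. Even then, what would be missed is a suspension for further analysis. The contradiction itself rests on the wording alone and needs no assumption about rates.

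**What to change.** Delete the seriousness statement from section 6.3, or add to it: *unless the event meets a criterion in 9.1.3*. If a dosing exception was intended, replace the sentence with: *Grade 3 or 4 electrolyte abnormalities corrected within 48 hours do not require a delay of cetuximab; seriousness is decided by section 9.1.3.* That version settles both dosing and seriousness.

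The cost is one sentence in an amendment, and possibly a few more SAE reports, which section 9 already requires.
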